## **9.4. Analysis Plan**

### **9.4.1. Subject Disposition and Baseline Characteristics**

A listing of all ITT analysis set subjects will be generated to describe site, subject number, first screening date, first treatment date, subject stratification, randomized treatment arm assignment (Arm A or Arm B), actual treatment arm allocation (Arm A or Arm B), the longest duration of study drug and ofatumumab treatment, and the reason for discontinuing study treatment. Available information on subjects who were screened or registered but not randomized or not treated will be listed separately. A table will be created summarizing these categories in terms of number and percent for the ITT analysis set.

Subject baseline characteristics will be listed and summarized by treatment arm and stratification factor for the ITT and responding analysis sets. Baseline data (eg, from the CIRS or FACT-Leu) will not be reconciled with other medical information (eg, adverse event data or past medical history data). Efficacy Analyses

#### **9.4.1.1. Primary and Supportive Analyses of the Primary Endpoint**

For the primary efficacy analysis, the difference in PFS between the treatment arms will be assessed in the ITT analysis set using Kaplan-Meier methods and the stratified log-rank test, adjusted for the stratification factors. Medians, ranges, the proportion of subjects who are progression-free at 24 and 48 weeks from randomization (based on Kaplan-Meier estimates), hazard ratios and corresponding 95% CIs (as calculated using a Cox proportional hazards regression model) will be presented.

The following exploratory sensitivity analyses will be performed:

- PFS will be compared between the treatment arms in the ITT analysis set using Kaplan-Meier methods and an unstratified log-rank test.
- PFS will also be compared between treatment arms in the PP analysis set using Kaplan-Meier methods and a stratified log-rank test.
- PFS will be further analyzed by censoring data from surviving, non-progressing subjects only at the last time that lack of definitive CLL progression was objectively documented. An additional worst-case sensitivity analysis will be performed in which surviving, nonprogressing subjects who are lost to follow-up are categorized as having an event at the time of the last known CLL tumor status assessment if they were in Arm A and are categorized as censored at the time of the last known CLL tumor status assessment if they were in Arm B. These analyses will be performed in the ITT analysis set using Kaplan-Meier methods and the stratified log-rank test.

The Cox regression approach will be used to explore the influences of the stratification factors, other baseline characteristics, and treatment on PFS. Beyond the stratification variables, additional baseline subject characteristics may be included as covariates, focusing on those with expected prognostic significance, particularly if these show imbalance between treatment groups. For the Cox regression modeling, a stepwise selection process will be applied to these variables to identify the final subset of relevant factors. Each prognostic factor will be preliminarily evaluated in the Cox regression model. Only the variables significant at the 0.20 level will be considered to build the multivariate model. A forward selection process will be applied to these variables to identify the final subset of relevant factors. Once a model has been established, treatment will be added to the final subset of factors to study its effect on the model. Treatment-by-factor interactions will be explored for the subset of factors included in the final model.

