#### **3.3. Primary Endpoint**

- Progression-free survival (PFS) – defined as the interval from randomization to the earlier of the first documentation of definitive disease progression or death from any cause; definitive disease progression is CLL progression based on standard criteria, other than lymphocytosis alone

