### 7.3. Timing of Assessments

During screening, clinical and imaging-based tumor assessments should be performed within the specified screening period. Clinical tumor assessments should be performed at each designated clinical visit (see [Appendix 7](#)). On-study CT/MRI tumor assessments should be performed as indicated in [Appendix 7](#), until ~129 events have been observed in the study population. An end-of-study CT/MRI tumor assessment should be performed unless the subject already has radiographic confirmation of disease progression  $\leq 4$  weeks prior. If a subject permanently discontinues study drug prior to objective documentation of CLL progression, investigators should continue further follow-up according to the protocol specified schedule until CLL progression is documented by the central IRC.

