#### 9.3.2.2. Calculation of Tumor Control and Patient Well-being Variables

Tumor control assessments will be based on standardized IWCLL criteria {[Hallek 2008](#)}, as specifically modified for this study considering the pharmacology of idelalisib and ofatumumab. The individual and composite endpoints of response and progression (considering changes in lymph node area, liver and spleen size, bone marrow, platelet counts, hemoglobin, neutrophil counts, and peripheral blood lymphocyte counts) will be determined. Tumor control will be documented at each assessment by response category (eg, CR, PR, SD, definitive PD, NE, ND) as defined for each response parameter, SPD value, percentage change in SPD values from baseline or nadir, date that response is first documented, date that response is confirmed, and date of definitive CLL progression.

The date of definitive CLL progression will be the timepoint at which progression is first identified by relevant objective radiographic or laboratory data. Where imaging data are available, these data will supersede physical examination data in determining tumor status. For purposes of analysis, subjects who have only physical examination evidence of definitive disease progression that is not confirmed by CT/MRI will be considered to have progressed at the time of the physical examination finding. Because of the characteristic redistribution lymphocytosis that expected with PI3K $\delta$  inhibition, lymphocyte count will be ignored in the evaluations of progression.

Changes in tumor status as provided by the investigator and changes in tumor status as adjudicated by the IRC (see Section [10.4.2](#)) will be described. The findings of the IRC will be considered primary for analyses of PFS and other tumor control endpoints.

The following censoring conventions will be applied:

- PFS: Data from surviving, non-progressing subjects will be censored at the earliest of the time of initiation of antitumor treatment other than the study treatment or the last time that lack of definitive CLL progression was objectively documented. Data from subjects who have CLL progression or die after  $\geq 2$  consecutive missing tumor assessments will be censored at the last time prior to the missing assessments that lack of definitive CLL progression was objectively documented.

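### The worst-case PFS analysis leaves censored those Arm A subjects known to have progressed or died after two or more missed tumor assessments, and on the natural reading no listed sensitivity analysis tests that censoring rule

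*Protocol*

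**What the plan says.** Section 3.3 ends PFS at "the earlier of the first documentation of definitive disease progression or death from any cause". Section 9.3.2.2 sets the PFS censoring conventions and limits that definition. A subject whose progression or death comes after two or more "consecutive missing tumor assessments will be censored at the last time prior to the missing assessments that lack of definitive CLL progression was objectively documented".

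Section 9.4.1.1 lists the sensitivity analyses and labels them exploratory:

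- an unstratified log-rank test in the ITT set;
- a stratified test in the per-protocol set;
- a change of censoring time: "PFS will be further analyzed by censoring data from surviving, non-progressing subjects only at the last time that lack of definitive CLL progression was objectively" (last word of the sentence omitted);
- the worst case: "An additional worst-case sensitivity analysis will be performed in which surviving, nonprogressing subjects who are lost to follow-up are categorized as having an event", dated to when tumor status was last known, when assigned to Arm A, whereas those in Arm B stay censored.

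On what counts as a tumor assessment, section 7.3 uses the term for more than scans: "Clinical tumor assessments should be performed at each designated clinical visit". It then treats CT/MRI tumor assessments separately.

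**The concern.** A worst-case analysis is meant to show that the PFS result survives the least favourable treatment of missing follow-up in Arm A. Here the reassignment is limited to subjects whose outcome is unknown. Subjects whose bad outcome is known, but came after a gap, keep the more favourable treatment. The analysis is thus stricter on an Arm A subject of unknown status than on one known to have failed.

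The other listed analyses do not fill the hole. The unstratified and per-protocol runs change the test or the analysis set. The third bullet, read naturally, only drops censoring at the start of other antitumor treatment. The one convention that departs from counting death from any cause is therefore never varied. A later statement that the PFS result holds in the worst case would claim more than the analysis shows.

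**Working it through.** **1. The plan's own figure.** Section 9.5 gives 129 events, HR 0.57, 2-sided alpha 0.05 and 170:85 allocation. By Schoenfeld's formula, z = √(129 × 2/3 × 1/3) × |ln 0.57| − 1.960 = 5.354 × 0.562 − 1.960 = 1.05, so power is 0.853. This reproduces the stated power above 0.85. The point concerns the censoring rule, not this figure.

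**2. The rules applied to three Arm A subjects with the same last assessment.**

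| Subject | Primary analysis | Worst case as written |
|---|---|---|
| Lost alive, not progressed | Censored at last assessment | Event at last assessment |
| Misses two or more assessments, then known to have progressed or died | Censored at last assessment before the gap | Still censored there |
| Dies after none or one missed assessment | Event at death | Event at death |

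The second row is the fault. It follows because section 9.3.2.2 sets the rule for PFS generally and section 9.4.1.1 changes it only for surviving, nonprogressing subjects.

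**3. Can such events be known?** Deaths can: section 6.2.16 collects survival status yearly for five years. Section 3.5.1 schedules scans at Weeks 8, 16, 24, 36 and 48 and every 12 weeks thereafter, so two missed scans span about 16 weeks early on and 24 weeks later.

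**4. Size in the worst-case analysis.** The protocol does not say how many events follow a gap, so the share of subjects who stop assessments is an assumption, taken as 5% to 30%. The simulation used:

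- 170 v 85 subjects, exponential PFS with medians of 14 and 8 months (8/14 = 0.571), and section 9.5's accrual pattern;
- a data cut at 24 months;
- stopping unrelated to outcome and uniform over each subject's follow-up, with a gap of 5.5 months (about 24 weeks) required;
- all later events taken as known;
- unstratified Cox and log-rank, with 1,500 runs per scenario.

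Corrected means that Arm A post-gap events also count, at the last assessment.

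| Share stopping | Arm A post-gap events | Arm A lost alive | HR as written | HR corrected | Difference | Runs significant at 0.05, written v corrected |
|---|---|---|---|---|---|---|
| 5% | 0.9 | 3.5 | 0.591 | 0.597 | 0.006 | 90% v 89% |
| 10% | 1.7 | 7.2 | 0.613 | 0.625 | 0.012 | 86% v 83% |
| 20% | 3.5 | 14.4 | 0.659 | 0.682 | 0.023 | 74% v 67% |
| 30% | 5.2 | 21.6 | 0.705 | 0.740 | 0.035 | 59% v 49% |

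On the log scale, the 10% row is ln(0.625/0.613) / |ln 0.57| = 0.0194 / 0.562, about 3% of the planned effect. The 30% row is 0.0485 / 0.562, about 9%. These runs average 155 to 161 events rather than 129, so the differences between columns matter more than the absolute shares of significant runs.

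**5. Size in the primary analysis.** In the same runs, counting post-gap events at their own date moves the HR from 0.571 to 0.573 at 10% stopping and from 0.574 to 0.581 at 30%. It would move more only if gaps were related to outcome and concentrated in one arm. As an illustration, section 9.5's assumptions cut at 129 events give about 75.3 v 53.7 events over 1,518 v 620 person-months, a rate ratio of 0.573. Four extra events in Arm A alone would give (79.3/1,518) / (53.7/620) = 0.603, and five would give 0.611. The four and five are hypothetical; nothing in the protocol supplies them.

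**The case against.** Censoring events after two or more missed assessments is standard practice, and extra PFS sensitivity analyses are commonly left to the SAP. Both points stand. The primary rule is therefore not treated as an error, and the mere absence of an additional analysis would not be a finding. What remains is an analysis that this protocol does specify and names a worst case, whose stated rule does not deliver one.

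No sentence says that the missed-assessment rule carries into the worst case. The word *only* in the third bullet could also be read as confining all censoring to surviving, non-progressing subjects, which would count post-gap events. This stands as a possible reading. It is less natural than taking the bullet to remove censoring at new therapy, and even then the worst-case sentence does not say that late events count.

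The simulated size also leans on generous assumptions. Follow-up under section 6.2.16 recovers deaths rather than scan-based progressions, and PFS progression rests on the IRC (section 7.1). Sections 5.9 and 7.3 continue assessments after study drug stops, which limits gaps. Subjects with a known late death are not the same group as the 10% lost to follow-up in section 9.5. All this stands and argues for the lower end of the range.

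A reader might infer that two missed weekly clinic visits are enough to discard a death, because section 7.3 speaks of clinical tumor assessments. The documents give this little support. Section 3.5.1 uses tumor assessments for the scan schedule, the visit tables (for example Table 6-7) place CT/MRI under the tumor assessment heading, and section 7.5.5 ties non-evaluability to images. The broader use in section 7.3 justifies a clarification and no more.

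**Conclusion.** The point holds in a limited form. On the natural reading, the worst-case analysis omits Arm A subjects known to have progressed or died after two or more missed assessments, so it is not a worst case, and no listed analysis varies the missed-assessment rule. With stopping unrelated to outcome, assumed at 5% to 30%, the worst-case HR is too favourable by about 0.006 to 0.035, and by about 0.012 at 10%.

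A reader might go further and infer that the primary HR is biased towards Arm A, since section 5.4.7 reports serious and fatal infections on idelalisib. The documents do not support this. They do not show that such deaths follow long gaps, or that gaps are commoner in Arm A. A death after none or one missed assessment counts as an event, and the OS analysis counts every known death. The formal primary test is untouched by the worst-case wording, and the affected analyses are exploratory. The priority is minor.

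**What to change.** In section 9.4.1.1:

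- state that in the worst-case analysis Arm A progressions and deaths after two or more missed assessments also count as events, while those in Arm B stay censored;
- add one PFS analysis that counts every known progression or death at its own date, regardless of gaps.

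In section 9.3.2.2, specify that the missed assessments are consecutive scheduled CT/MRI assessments. The primary censoring rule otherwise stays.

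The cost is a wording change, one extra run on data already collected, and a worst-case figure that may be slightly less favourable.

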#### 9.4.1.2. Other Time-to-Event Tumor Control and Survival Endpoints

Differences between the treatment arms in TTR, DOR, and OS will be assessed in the appropriate analysis set using Kaplan-Meier methods and stratified log-rank tests. Medians, ranges, hazard ratios and corresponding 95% CIs will be presented.

A supportive Cox regression analysis of OS in the ITT analysis set will be performed using the same methods as in the analysis of PFS if a sufficient number of events occur.

Sensitivity analysis for ORR, CR rate, DOR, and TTR will be performed based on responses without the need for confirmation.

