#### **3.4. Secondary and Exploratory Endpoints**

The following secondary and exploratory endpoints will be defined and analyzed in this study. Five endpoints are designated as secondary endpoints for which sequential testing will be performed to control Type I error rate (see Section 9.4.1.6). Secondary endpoints will be ORR, lymphadenopathy response rate, OS, PFS in the subgroup of subjects with 17p deletion and/or TP53 mutation, and CR rate. All other endpoints will be considered exploratory.

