### **9.3. Analysis Conventions**

#### **9.3.1. Analysis Sets**

##### **9.3.1.1. Intent-to-Treat Analysis Set**

The ITT analysis set includes data from all subjects who are randomized regardless of whether subjects receive any study drug(s), or receive a different regimen from that to which they were randomized. Study drug assignment will be designated according to randomization.

This analysis set will be used in the analyses of subject characteristics, PFS, ORR, OS, CR rate and health outcome variables. The analysis of PFS based on the ITT analysis set will be considered the primary analysis of the study. Subjects in the ITT analysis set who do not have sufficient baseline or on-study tumor status information to be adequately assessed for response status (ie, those with best overall responses of NE or ND) will be included in the denominators in calculations of response rates.

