#### 9.4.1.6. Control of Type I Error Rate in Efficacy Analyses

In the efficacy analyses, the following procedures will be implemented to preserve the overall type I error rate across the primary and secondary endpoints of the study at a 2-sided significance level of 0.05.

The primary endpoint analysis will serve as the gatekeeper for the secondary endpoint analyses, ie, the primary efficacy hypothesis must be made before the efficacy hypotheses for the secondary efficacy endpoints can be tested. The secondary endpoints will be the following:

- ORR
- Lymphadenopathy node response rate
- CR rate
- OS
- PFS in the subgroup of subjects with 17p deletion and/or TP53 mutation

If the primary hypothesis is rejected, the 5 secondary endpoints will be sequentially tested at the 2-sided 0.03 significance level in the order listed above. If a null hypothesis is not rejected, formal sequential testing will be stopped and only nominal significance will be cited for the remaining secondary endpoints. Analyses and p-values will be reported for all the efficacy endpoints, including the primary endpoint, the secondary endpoints, and all of the exploratory endpoints.

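### The planned log-rank test and hazard ratio for duration of response compare responders only, so they are not a randomised comparison

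*Protocol*

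**What the plan says.** Protocol 9.4.1.2 handles DOR in the same sentence as overall survival: "Differences between the treatment arms in TTR, DOR, and OS will be assessed in the appropriate analysis set", by Kaplan-Meier methods and stratified log-rank tests. It adds: "Medians, ranges, hazard ratios and corresponding 95% CIs will be presented". Section 9.4.1.6 says: "Analyses and p-values will be reported for all the efficacy endpoints", and the exploratory endpoints are expressly included. Section 9.3.2.1 sets a default two-sided 0.05 level.

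DOR is not one of the five secondary endpoints in 3.4, which adds: "All other endpoints will be considered exploratory". Section 9.3.1.1 lists what the ITT set is for: "This analysis set will be used in the analyses of subject characteristics, PFS, ORR, OS, CR rate and health outcome variables". DOR and TTR are not in that list. The DOR censoring rule in 9.3.2.2 covers surviving subjects without progression and gives non-responders no value. Under 7.5, a CR or PR must last at least 8 weeks before it counts as confirmed.

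No visible text calls the DOR comparison descriptive or warns that it is not randomised. The endpoint definitions that would cover DOR and TTR appear to be among the redacted items in 3.4.1.

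**The concern.** A log-rank test has its usual meaning when randomisation formed the two groups. For DOR the groups are formed later, by who responds. If idelalisib raises the response rate, Arm A's responders include subjects who would not have responded in Arm B. Those subjects plausibly have worse prognosis, so Arm A's responders would be a less favourable mix even if the drug had no effect on how long a response lasts. Stratifying on the three randomisation factors does not remove differences in other prognostic features.

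At stake is the reading of one exploratory result. Duration of tumour control belongs to a stated secondary objective, and 3.5.1 names DOR as important for describing it. A hazard ratio and p-value printed in the same format as those for survival invite a causal reading that they cannot bear.

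**Working it through.** The plan gives no sample size, event count or power for DOR, so there is no figure to reproduce. The check asks what the planned contrast shows when the drug has no effect on duration.

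**Inputs from the protocol**
- Allocation 170:85 (9.5); two-sided 0.05 (9.3.2.1).
- Response to ofatumumab alone: 58% and 47%, in two groups of the pivotal Phase 2 trial (1.1).
- Response to idelalisib plus ofatumumab: 16/21 = 76%, Phase 1 (1.3.5.2.2).

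The protocol assumes no response rate for either arm of this trial. These rates are borrowed for illustration.

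**Who enters the test at those rates**
- Arm A: 0.76 × 170 ≈ 129 responders; 24% of the arm is left out.
- Arm B: 0.47 × 85 ≈ 40, or 0.58 × 85 ≈ 49; 53% or 42% is left out.

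**Assumptions not in the protocol**
- A latent standard-normal prognosis U decides response: the best 76% of Arm A respond, and the best 47% or 58% of Arm B.
- Duration is exponential, with median 14 months at U = 0 and log-hazard falling by β per SD of U.
- Censoring is uniform over 10 to 22 months.
- The log-rank test is unstratified and made in responders only; 4,000 trials per scenario.

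**Simulated results, no treatment effect on duration**

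| β | 76% vs 47%: median HR | rejects | 76% vs 58%: median HR | rejects |
|---|---|---|---|---|
| 0 | 1.01 | 5.4% | 0.99 | 4.8% |
| 0.3 | 1.14 | 6.7% | 1.09 | 6.0% |
| 0.6 | 1.29 | 13.8% | 1.17 | 8.6% |
| 1.0 | 1.50 | 29.4% | 1.28 | 15.6% |

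An HR above 1 is against Arm A.

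**Control case.** With 58% response in both arms and β = 1.0, the median HR is 1.00 and the test rejects in 4.2% of trials. Under this model, selecting on response distorts the contrast only when the rates differ.

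**With a true benefit.** Give idelalisib a true HR of 0.70 on duration at 76% vs 47%. With β = 0 the median observed HR is 0.67. With β = 1.0 it is 1.14.

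**Hand check.** The mean of U among the best fraction r is φ(z)/r, where z is the (1 − r) normal quantile and φ the normal density.
- r = 0.76: 0.311/0.76 = 0.41
- r = 0.47: 0.398/0.47 = 0.85
- r = 0.58: 0.391/0.58 = 0.67

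Arm B's responders are therefore better by about 0.44 SD (47%) or 0.26 SD (58%). The approximate spurious HR is exp(β × difference). At β = 0.6 this gives exp(0.6 × 0.437) = 1.30 and exp(0.6 × 0.265) = 1.17, against the simulated 1.29 and 1.17.

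**The case against.** Four points can be made for the plan.

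**DOR is exploratory.** No alpha, sample size or confirmatory claim depends on it, and PFS in the ITT set gives a randomised view of tumour control beside it. This stands and limits the weight of the point.

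**The analysis set is left open and may be settled in the SAP.** Section 9.4.1 mentions a responder set ("for the ITT and responding analysis sets"), but only for baseline characteristics, and 9.3.1 does not define it. That phrase is therefore weak evidence of the set meant for DOR. It does not rescue the test: non-responders have no DOR, so any set reduces to responders, and the protocol itself already fixes the test and hazard ratio.

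**The size depends on assumptions.** This also stands. The ofatumumab rates come from fludarabine-refractory patients who were also alemtuzumab-refractory or had bulky nodes. The 76% is investigator-reported in 21 subjects. This trial uses independent review and requires the response to be maintained. With no link between prognosis and duration, there is no inflation.

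**TTR is a different case.** A reader might extend the criticism to TTR because 9.4.1.2 names it in the same sentence. The documents do not support that. The synopsis says exploratory tumour-control endpoints use the ITT, PP or pharmacodynamic sets and that time-to-event endpoints are analysed much as PFS is; the TTR definition is not visible. With all randomised subjects included and non-responders censored or treated as a competing event, TTR is a randomised comparison.

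**Conclusion.** The point holds for DOR. The protocol prescribes a between-arm test, hazard ratio and reported p-value for a quantity that exists only in a subset formed after randomisation, and no choice of analysis set changes that.

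The size is illustrative. At the borrowed response rates, and with β from 0.3 to 1.0, the median HR under no effect is 1.09 to 1.50 and the 5% test rejects in 6.0% to 29.4% of trials. These figures rest on the assumed link between prognosis, response and duration and on rates taken from different studies.

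Two stronger readings should be resisted. One is that the test could just as well favour idelalisib falsely: the calculations show a shift against Arm A only, so in this model the error understates benefit. The other is that the trial's main conclusions are at risk: the primary PFS analysis and the five gatekept secondary tests are untouched. This is an inexpensive improvement to an exploratory analysis.

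**What to change.** In 9.4.1.2, take DOR out of the sentence on between-arm tests. Report it by arm among responders, with Kaplan-Meier estimates and CIs and no log-rank test or hazard ratio. In 9.4.1.6, exempt DOR from the statement that p-values will be reported.

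If a between-arm comparison of duration is wanted, use a quantity defined for every randomised subject, such as mean time in response up to a fixed time, with zero for non-responders.

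Keep the TTR comparison if it is made in all randomised subjects, and say so. If it is restricted to responders, make it descriptive as well.

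The cost is a wording change and the loss of one exploratory p-value and hazard ratio. No data collection, sample size or alpha allocation changes.
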